to investigate patients' adherence with diseases of the global airways, and analyse whether patients' adherence with diseases of the global airways can be improved and whether this will contribute to increased disease control and significantly improved quality of life.

Purpose

To investigate the effect of systematic and structured nursing guidance in patients with global airways disease, CRSwNP and asthma primarily on adherence (measured on MARS-5- L/N), where the maximum score is 50 at 100% adherence for both diseases. As well as whether there is a change at the minimum in adherence in patients who receive systematic and structured guidance on disease and treatment compared to usual care which does not include structured guidance.

Hypothesis and research questions

Patients with respiratory diseases can improve their adherence to their non-medical and the medical treatment for CRSwNP/CRS and asthma by systematic and structured nursing guidance compared to patients who did not receive the above guidance.

In a randomized study, we will investigate whether the level of adherence measured by the questionnaire MARS-5-N and MARS-5-L in patients with CRSwNP/CRS and asthma can be improved by 5 points after systematic and structured nursing guidance at baseline visit and controlled after four months - compared with those patients who have not received the above guidance.

Outcomes

The primary outcome is to investigate whether the adherence rate measured by the MARS-5-N/L questionnaire in patients with CRSwNP and asthma can be improved by 4 points after systematic and structured nursing guidance at the initial visit and controlled after four months - compared with those patients who have not received the above guidance.

Secondary outcomes

- To demonstrate whether improved adherence can improve their sleep measured on a Epworth Sleepiness Scale - messured during a 4 month follow-up visits.

- To demonstrate whether improved adherence can improve their SNOT22 score by 9 points or more messured at a 4 month follow-up visits.

- To demonstrate whether improved adherence can improve their asthma control as measured by the ACQ messured at a 4 month follow-up visits.

- To demonstrate whether improved adherence can improve their asthma control as measured by ACT - measured at a 4 months follow-up visit.

- To demonstrate whether improved adherence can improve their quality of life as measured by the mini AQLQ messured at a 4 months follow-up visit.

06.05.2022

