- To demonstrate whether improved adherence can improve their anxiety/depression as measured by HADS - messured at a 4 months follow-up visit.

- To demonstrate whether satisfactory adherence (i.e. 80%) can improve their nasal symptoms measured via SNOT22 and STARR-15 - messaured at 4 a months follow-up.

- To demonstrate whether satisfactory adherence (i.e. 80%) on lung measured via MARS-5-L and poor adherence on nose measured via MARS-5-N improve their respiratory symptoms measured ACQ or ACT - messsured at a 4 months follow-up.

- Demonstrate differences in patients with three conditions (asthma, CRS and allergic rhinitis) measured via STARR-15 meassured at a 4 months follow-up visit.

Background

CRS is a condition of chronic inflammation of the nose and sinuses. CRS can appear in the nasal polyps (CRSwNP) and without polyps (CRSsNP)(2,3). 9% of the Danish population is affected by CRS, and approximately 4% are estimated to be diagnosed with CRSwNP (4). The diagnosis is based on the patient's symptoms and objective signs of inflammation in the nose and sinuses. Symptoms include nasal congestion or nasal secretion that runs forward or backward, decreased air passage, decreased sense of smell, pain/pressure around the nose, forehead or eyes. For the diagnosis to take place, the above symptoms must have been present for more than 12 weeks. To diagnose CRS, there must be secretions or reduced air passage through the nose (6,7). Approximately 40% of CRS patients in primary care have asthma, whereas 65% referred to hospital have asthma (8).

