The term adherence describes the patient's compliance with the treatment strategy developed in consultation with a practitioner. The patient is considered an active participant in his or her treatment. Adherence can be measured for both pharmacological and non-pharmacological treatment. The WHO classifies measures of adherence as subjective and objective (13,14). Objective measures include measures such as pill counts, electronic monitoring (common medical card) or biochemical measures (e.g. blood tests) (13). Subjective measures include those that require assessment by, for example, the doctor, nurse or patient. Self-reporting by the patient or assessment by the healthcare professionals are the most common methods used to assess patient adherence. MARS-5 is a subjective tool that can be used to measure patient adherence - developed by [name] (15,16). The MARS-5 is a generic tool. It has been validated in many different clinical settings, e.g. in patients with asthma (17). The MARS-5 consists of five questions describing patient adherence to their medical treatment. Question 1) "I forget to take them", question 2) "I change the dose", question 3) "I stop taking them for a while", question 4) "I decide to skip a dose" and question 5) " I take less than instructed". Patients are asked to rate their adherence to their medication on a 5-point scale ranging from "always" to "never" (1-5 points). The total score on the scale goes from 5 (lowest compliance) to 25 points (macsi-mal compliance).

Poor adherence is particularly seen in long-term treatment among chronic patients, underlining the importance of focusing on sustained adherence in these patients (18). Some patients stop their treatment when they have symptoms under control, after which an exacerbation occurs. They resume their treatment with the feeling that "it is not helping" because they get worse (19). The WHO estimates that only 50% of patients receiving long-term pharmacological treatment for their chronic diseases are adherent to their treatment (19,20). Adherence in asthma and COPD has been shown to vary between 22%-78% (5,19). Patients with asthma receive information, guidance, and training related to their disease in the context of "usual care" in many places. Patients' adherence to pharmacological treatment depends on their age, their level of education, their knowledge of asthma, how often they have to take medication, whether the medication is easy to take,

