and how their communication is with the practitioner (19,20). Adherence to inhaled medications is lower than to oral tablets or injectable medications. The more complex and the more times the patient has to remember to take the medication, the harder it is to establish optimal adherence (19,20).

CRSwNP a chronic disease like asthma, where low adherence is often seen in mild to moderate cases compared to severe cases of CRSwNP (21). However, the clinical perception is that not all patients take all their daily doses, but few scientific studies have focused on this. The difficulty in treating CRS is that the patient must apply nasal steroid 1-2 times daily as well as it must be combined with nasal saline irrigation at least once daily. Decreased adherence is led by poor disease control. It is therefore important to support and strengthen patient adherence to CRS and asthma in order to achieve good disease control (21).

Population and recruitment

The study population consists of patients referred to the Respiratory Clinic in the Department of Ear, Nose and Throat Surgery and Audiology, Rigshospitalet. Patients are recruited by initial visits to the Respiratory Clinic, where they receive oral and written information about the project. If patients wish to participate, they must complete a written consent form for participation in the project. In order to be included in the study, the following inclusion and exclusion criteria must be met:

Inclusion criteria	Exclusion criteria
Adherence to MARS- 5 L/N ≤35	Adherence to MARS-5- L/N >35
at first visit	points at first visit
Diagnosed with asthma (with and	Do not have smartphone
without allergic rhinitis) at initial	
visit	
Able to use smartphone	Does not read or speak English
Able to use smartphone	Does not read of speak Elignish
ACQ \geq 1.2 or ACT \leq 15 (partially	Other illness requiring regular
uncontrolled asthma)	medication
Be over 18 years of age	Pregnancy and pregnancy that
	started during the study time pe-
	riod
SNOT-22 score ≥35	Servere psychological comorbidi-
	ties
Diagnosed with CRSwNP	

Material and method

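### Eight of nine secondary outcomes are framed by adherence and none by randomised arm; the two built on 80% adherence are non-randomised comparisons with incompletely defined groups

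*Combined protocol and SAP*

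**What the plan says.** All places are in the combined protocol and SAP.

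- **Outcomes.** The primary outcome names its comparator: adherence is "controlled after four months - compared with those patients who have not received the above guidance".
- **Secondary outcomes, six items.** These ask whether improved adherence changes a score (Epworth, SNOT-22, ACQ, ACT, mini AQLQ, HADS). An example is "To demonstrate whether improved adherence can improve their SNOT22 score by 9 points or more". No arm is named.
- **Secondary outcomes, two items.** These are built on an 80% level. The first is "To demonstrate whether satisfactory adherence (i.e. 80%) can improve their nasal symptoms measured via SNOT22 and STARR-15". The second asks whether satisfactory adherence "on lung measured via MARS-5-L and poor adherence on nose measured via MARS-5-N improve their respiratory symptoms", scored by ACQ or ACT.
- **Secondary outcomes, ninth item.** It compares STARR-15 across three disease conditions, so it is framed neither by adherence nor by arm.
- **Population and recruitment.** Entry requires "Adherence to MARS- 5 L/N ≤35" at the first visit. This must be the pooled score, since one scale stops at 25.
- **Material and method.** MARS-5-N and MARS-5-L are scored at the initial visit and at four months. The section equates 41 points with 80% of the pooled total and sets satisfactory adherence at 80%.
- **Statistics data analysis and power calculation.** Paired and unpaired tests, with rank-based counterparts, are listed without saying which groups they compare. The second sample-size scenario uses another rule: each of the two scales exceeding 80%.

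**The concern.** Randomisation protects a comparison of guided with unguided patients. It does not protect a comparison of patients who became adherent with patients who did not. Whatever makes a patient adhere may also bear on symptoms, and the protocol's Adherence section names candidates: age, education, knowledge of asthma, and disease severity ("low adherence is often seen in mild to moderate cases compared to severe cases of CRSwNP"). It also notes that "Some patients stop their treatment when they have symptoms under control, after which an exacerbation occurs". If the two 80% outcomes are analysed as worded, a difference in SNOT-22, STARR-15, ACQ or ACT could reflect who adheres, and the aim of demonstrating an effect would not be met whichever way the result fell.

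The second risk is flexibility. Where the scale, the cut-off or the classifying visit is left open, the satisfactory and poor groups can be settled after the data are seen.

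**Working it through.** **1. The plan's own cut-off.** Inputs: two scales of 5 to 25 (Adherence section), pooled maximum 50, stated cut-off 41 (Material and method).
- 80% of the pooled maximum: 0.80 × 50 = 40.
- Stated cut-off: 41 / 50 = 82%.

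The stated figure is not reproduced. 41 is the lowest whole score strictly above 80%, but the text presents it as equal to 80%.

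**2. Can satisfactory status exist at entry?** Input: pooled score of 35 or less.
- Pooled rule: needs 40 (at least 80%) or 41 (above 80%). Both exceed 35.
- Both-scales rule: one scale at 80% is 0.80 × 25 = 20. At least 80% on each needs 20 + 20 = 40; above 80% on each needs 21 + 21 = 42. Both exceed 35.
- Single-scale rule: possible. For example, lung 22 and nose 12 total 34.

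There are 21 × 21 = 441 possible whole-score pairs, of which 321 total 35 or less. None of the 321 has both scales at 20 or more; 51 have lung at 20 or more, with nose then at most 15. These are counts of possible scores, not expected patients.

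So pooled or both-scales status can arise only after randomisation, and the four-month visit is then the only MARS-5 measurement that can define it. On a single-scale reading, either visit could.

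**3. Do the two rules pick the same patients?** Of the 55 pairs totalling 41 or more, 35 have both scales at 20 or more and 20 have one scale below 20 (lowest 16, as in 25 + 16). The rules differ.

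**4. Can either rule define the lung/nose outcome?** If, for illustration, poor on the nose means below 20, lung at 20 or more with nose below 20 gives 6 × 15 = 90 pairs. None meets a both-scales rule, and only 10 reach 41. Neither rule describes this group. The outcome names its scales, but no points cut-off for MARS-5-L, no definition of poor on MARS-5-N and no classifying visit. Its four months is attached to the symptom measure.

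**5. Does 41 enter the sample size?** With alpha 0.025 (taken as two-sided, since the plan does not say) and 80% power, (2.241 + 0.842)² = 9.505.
- Means: 2 × 9.505 × 6.28² / 5² = 29.99, so 30; 30 × 1.2 = 36, as stated.
- Proportions, 100% against 80%: (0 + 0.8 × 0.2) × 9.505 / 0.2² = 38.02, so 39; 39 × 1.2 = 46.8, so 47, as stated.

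Both stated sizes are reached without 41.

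**The case against.** The strongest reply is that the whole trial compares guidance with usual care. The title, the Purpose and the two-arm design say so, and unpaired tests are listed. The six improved-adherence outcomes are then loosely worded arm comparisons, following the chain from guidance to adherence to disease control. That is a fair reading and it stands: a reader might infer that every secondary outcome is planned as a non-randomised comparison, but the documents support that firmly only for the two 80% outcomes. The six still need the arms named.

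Other stronger readings also fail:
- *Satisfactory adherence is wholly undefined.* Not so. Material and method gives a pooled cut-off, though one point away from 80% and not carried into the outcomes list.
- *The classifying visit is open throughout.* It is open only on a single-scale reading, as the lung/nose outcome requires.
- *A patient entering at 35 who gains the targeted 4 or 5 points would still miss 41.* Those points are stated against unguided patients. A between-arm difference is not one patient's gain and cannot be added to an entry score.
- *The protocol shows that control drives adherence.* The sentence "Decreased adherence is led by poor disease control" is unclear. What follows it suggests that adherence affects control, which is the hypothesised effect and not confounding. Severity, education and asthma knowledge are the sounder examples.

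**Conclusion.** The point holds in this form. None of the nine secondary outcomes names the arms, and eight are framed by adherence. Two of those, as written, compare patients by adherence level. On a pooled or both-scales definition that level is reached only after randomisation; on a single-scale definition taken at entry, the groups are still not randomised ones. Such comparisons can describe associations, not demonstrate effects.

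The size and direction of confounding are unknown. The documents give neither the number of patients who would fall in each group nor an SD for any secondary scale, so the power of arm comparisons on these scales cannot be derived either. A reader might infer that the bias favours guidance; nothing in the documents fixes its direction.

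The 41-point sentence is a separate, minor error of one point (82% against 80%). A reader might infer that it undermines the primary outcome or the sample size; neither uses it.

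The conclusion rests on reading the entry limit of 35 as the pooled score and on whole-number scoring of each scale from 5 to 25.

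**What to change.** 1. For the eight adherence-worded outcomes, make the comparison of randomised arms at four months the main analysis. This amounts to seven scales: Epworth, SNOT-22, ACQ, ACT, mini AQLQ, HADS and STARR-15. State in the statistics section that the unpaired comparison is between arms.
2. Adjust for the baseline score where it is collected. SNOT-22, and ACQ or ACT, are needed for entry. For Epworth, mini AQLQ, HADS and STARR-15, adjustment is possible only if they are also completed at the first visit, which the documents do not show.
3. Label comparisons by achieved adherence as exploratory associations, and drop the claim to demonstrate an effect for them.
4. Correct the 41-point sentence: either 40 of 50 (at least 80%) or 41 and over (above 80%). State whether satisfactory means the pooled score or both scales, and use one rule throughout.
5. For the lung/nose outcome, give a MARS-5-L cut-off (80% of 25 is 20; say at least or above), a defined poor range on MARS-5-N, and the visit that classifies patients.

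The cost is rewording and a few extra model runs. No new data are needed for SNOT-22 or for whichever of ACQ or ACT is recorded at entry; adjusting the other scales may need first-visit questionnaires. The downside is weaker claims for the adherence-based comparisons.

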NCTXXXXXXX

Adherence in Global Airways - Difference Between Structured and Systematic Nursing Supervison vs Usual Care.

Abbreviations

ACT - Asthma Control Test ACO-7 Asthma Control Ouestionnaire Adherence - Patients adherence to their non pharmacological/pharmacological treatment CRS -Chronic Rhinosi Chronic sinusitis CRSsNP - Chronic sinusitis with no nasal polyps CRSwNP Chronic sinusitis with nasal polyps ESS - EPWORTH SLEEPINESS SCALE Global Airways - Lower and upper respiratory diseases (asthma, rhinitis and CRS/CRSwNP/CRSsNP) HADS - Hospital Anxiety and Depression Scale MARS-5 - Medication adherence report scale MARS-5-L - Medication adherence report scale - lung MARS-5-N - Medication adherence report scale - nose miniAQLQ - Mini asthma quality of life questionnaire miniRQLQ - Mini Rhino conjunctivitis Quality of Life Questionnaire RCT - Randomised Controlled Trial SNOT-22 - The Sino-Nasal Outcome Test 22 STARR-15 - Standard test for asthma, rhinitis and chronic rhinosinusitis (15 questions) ENT - Department of Ear, Nose and Throat Surgery and Audiology, RigsHospitalet

Introduction

There is a strong case for treating diseases of both the upper and lower airways (global airways) simultaneously, because they share the same inflammatory mechanisms (1,2). About 9% have chronic sinusitis (CRS) and 4% of the Danish population are diagnosed with (CRS) with nasal polyps (CRSwNP) and 7-10% have asthma. CRS has a multifactorial background, with CRSwNP characterized by Type 2 inflammation, and approximately 50% with Type 2 CRSwNP also have co-morbid asthma (3). Well-treated CRS has an impact on asthma control, and well-treated asthma has an impact on CRS.

The above can be strongly supported by daily clinical practice, where these patients experience high levels of morbidity, which often significantly affect their daily lives and thereby also result in a markedly reduced quality of life. Several studies show that patients with asthma have low adherence (4,5), but only a few if any of studies are available on adherence in CRS. Patients rely on seeing different specialists (otolaryngologist and pulmonologist) to optimize their adherence in the upper or lower airways. This provides an opportunity

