The study is a randomized trial with a control group and an intervention group. Patients will be randomized via Research Electronic Data Capture (Redcap), a secure web application for building and managing databases and online questionnaires. The system was developed at Vanderbilt University, which released the first version in 2008 (22). Patients will be randomized to the control or intervention group. Randomization will be stratified by gender. Patients in the intervention group will receive systematic and structured nursing guidance regarding their adherence, which includes proper use of nasal irrigation once or twice daily, nasal steroid/drops, use of inhaled medications, follow-up of smoking status. The intervention group will receive guidance videos which have been prepared prior to the study and will be standard for the intervention group. Guidance videos will cover the correct use of nasal irrigation, inhalation steroid, and nasal steroid/drops. The control group and intervention group will receive twice a week text message reminders to take their medications and to rinse their nose.

Their adherence will be measured via MARS-5-N and MARS-5-L f. Total MARS-5-N/L will be measured at their initial visit and four months after teaching or usual care. The same form will be given at both visits. Patients in the control group will not receive systematic and structured nursing care regarding their adherence, but their adherence will be measured via MARS-5-N and MARS-5-L max score is 50 when measuring a adherence in global airways. In a pilot study, mean (SD) 20.4 (6.28) is found for MARS-5-L, and for MARS-5-N mean 20.7 (5.57) is found. 41 points correspond to 80% of total of both MARS-5-L and MARS-5-N. A satisfactory adherence should be 80%. In another pilot study, patients were measured twice with at least one month in between. Here, the mean of the inter-individual difference at MARS-5-L/N first and second time is equal to 5.34(2.62). These two pilot studies will be used for the final power calculation.

Statistics data analysis and power calculation

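### The non-medical part of the adherence hypothesis has no measure of its own: MARS-5-L/N is described as a medication scale, and no listed outcome separately records nasal irrigation or smoking

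*Combined protocol and SAP*

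**What the plan says.** **What is claimed.** The Abbreviations section defines adherence as "Patients adherence to their non pharmacological/pharmacological treatment". Under Hypothesis and research questions, patients given the nurse-led guidance "can improve their adherence to their non-medical and the medical treatment for CRSwNP/CRS and asthma".

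**What is taught.** Under Material and method, the guidance is described as something "which includes proper use of nasal irrigation once or twice daily, nasal steroid/drops, use of inhaled medications, follow-up of smoking status". Both arms also receive, twice a week, "text message reminders to take their medications and to rinse their nose".

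**What is measured.** Outcomes states: "The primary outcome is to investigate whether the adherence rate measured by the MARS-5-N/L questionnaire". The score is taken at the first visit and after four months, on the same form both times. On the tool, the Adherence section says: "The MARS-5 consists of five questions describing patient adherence to their medical treatment". It continues: "Patients are asked to rate their adherence to their medication on a 5-point scale". The five items it lists are about forgetting, altering the dose, stopping for a time, skipping a dose and taking less than prescribed. Each scale runs from 5 to 25, and the lung and nose scales together give a maximum of 50.

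**What points the other way.** The Background section on CRS names saline irrigation, beside nasal steroid, as part of basic medical treatment.

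**The concern.** The hypothesis has two parts, medical and non-medical, and the plan names one instrument, which it describes in terms of medication. The Adherence section itself notes that adherence to non-pharmacological treatment can be measured, but no instrument for it is named.

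This matters in three ways:

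- A positive MARS-5-L/N result could be read as support for the whole hypothesis when one part had no measure of its own.
- The Background presents the daily combination of rinsing and nasal steroid as the difficulty in treating CRS. If guidance changed rinsing but not spray use, the trial might not see it, or could not say that this was what changed.
- Several secondary aims ask whether improved adherence improves symptoms such as SNOT-22. A change in rinsing could move those symptoms without being recorded, and the result would then be credited to medication or left unexplained.

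**Working it through.** This is a question of coverage, so the main check sets the sections side by side. A short calculation then shows what the sample size does and does not cover.

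**Step 1. Guidance components against the measures.**

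- Inhaled medication: within MARS-5-L as described.
- Nasal steroid/drops: within MARS-5-N as described.
- Nasal irrigation: not named in any of the five listed items. Whether MARS-5-N covers it is not stated.
- Smoking status: not in the listed items, and not a matter of dosing.

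**Step 2. Other outcomes.** The nine secondary outcomes concern sleepiness, SNOT-22, ACQ, ACT, mini AQLQ, HADS, nasal symptoms at satisfactory adherence, respiratory symptoms when lung adherence is good and nose adherence poor, and STARR-15 across the three conditions. They measure symptoms, disease control, quality of life and mood. None records how often patients rinse or whether they smoke. The section on information from patient records says that none will be drawn from them, so the gap is not filled from that source.

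**Step 3. Both readings of MARS-5-N.**

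- *Irrigation is outside the scale.* Then no planned variable measures it.
- *Irrigation is inside the scale.* Then a rise in the nasal score may come from more spray, more rinsing or both. The plan analyses total scores, and pools nose and lung to 50 points, so the sources cannot be told apart.

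Under either reading, no planned comparison isolates non-medical adherence.

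**Step 4. The plan's sample size.** Inputs from the power calculation: difference 5, SD 6.28, alpha 0.025 (0.05/2; taken as two-sided, which the plan does not state), power 80%.

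- n per group = 2 × (2.2414 + 0.8416)² × (6.28/5)² = 2 × 9.505 × 1.5775 = 29.99, so 30.
- Adding 20%: 30 × 1.2 = 36, the stated figure. (Dividing by 0.8 gives 37.5, so 38.)

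The stated figure reproduces. Its difference and SD are in MARS-5 points, so the trial is sized only for what MARS-5 measures. The plan gives no effect size or SD for irrigation or smoking, so no power can be computed for them. In SD units, the 95% confidence interval for a difference in means has a half-width of about 1.96 × √(2/30) = 0.51 SD with 30 evaluable per group, and 1.96 × √(2/39) = 0.44 SD with the 39 of the plan's second calculation. Added items would therefore give estimates with moderate precision, not a powered test.

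**The case against.** The strongest reply is that the documents do not show that MARS-5-N leaves irrigation out. The Background places saline irrigation within medical treatment, and the Adherence section says MARS-5 concerns medical treatment. The listed items are those of the generic tool: they refer to the treatment by a pronoun, name no drug, and the nose version is not reproduced. This stands in part. In the Background, medical is set against surgical; the Adherence section also speaks of medication; and the reminders list rinsing apart from medicines. The text points both ways on irrigation, so a reader who infers that the scale certainly excludes it goes further than the documents allow.

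A reader might also infer bias: that guided patients will answer MARS-5-N for rinsing plus spray while controls answer for spray alone. The documents do not support this. Both arms complete the same form at both visits, and both are reminded to rinse. Only the intervention arm gets the teaching and videos, so a shift is possible, but nothing shows that it would occur, in which direction, or how large it would be.

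A reader might further give smoking the same weight as irrigation. The plan lists only follow-up of smoking status, the videos do not cover it, and smoking is not described as a treatment to which patients adhere. Its absence from the outcomes is certain, but it is the smaller part of the point.

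Finally, a trial need not have an outcome for every component it delivers, and the primary outcome is already framed in MARS-5-N/L terms. Both are fair. They limit the point to the hypothesis and the conclusions drawn from it, where non-medical adherence is explicitly claimed.

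**Conclusion.** The point holds in this form: the hypothesis and the definition of adherence include non-medical treatment, but no planned outcome measures it separately, so that part of the hypothesis cannot be tested as planned. This is firm, because it follows whether or not MARS-5-N captures irrigation. It rests on the protocol's own description of MARS-5, on the list of outcomes being complete, and on the analysis of total scores.

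The size is limited. The randomised comparison of MARS-5-L/N remains usable, no sample-size figure changes, and no bias in that comparison is shown. What is affected is the breadth of the claim and the ability to say which behaviour changed. It is a cheap improvement rather than a flaw in the primary comparison.

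**What to change.** 1. **Add two short items** to the REDCap questionnaires at baseline and month 4, in both arms: one self-report irrigation item (for example, days with irrigation in the last 7) and current smoking status. List both as secondary outcomes, compared by randomised arm with 95% confidence intervals. Tests already in the plan would serve: Mann-Whitney for irrigation days and chi-square for smoking status.
2. **State what MARS-5-N covers.** Reproduce its wording and say whether irrigation is included, in line with how the pilot used it. Narrowing the form to steroid/drops alone is not advised: it picks one reading without knowing the authors' intent, and could break comparability with the pilot figures (mean 20.7, SD 5.57).
3. **Limit the conclusion** from MARS-5-L/N to the adherence it measures, and let the new items speak for the non-medical part of the hypothesis.

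The items must be in place before patients complete the baseline forms, because baseline answers cannot be collected afterwards.

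The cost is two short items at two existing visits, two secondary outcomes beyond the nine listed, and a narrower headline claim. No extra visits or patients are needed. The new comparisons should be presented as secondary estimates, since the trial is not sized for them.
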